Day	-7				1	2	8*	15*	22*	29*	43*	57*		Study Day 9).
Window (days)	-6				0	0	+5	+5	+5	+5	+5	+5	+5	** Not performed as of amendment 1
Biomarker blood sample (FVIII, FIX, FXII, vWF antigen, vWF activity)					•									See Section 8.8
Immunogenicity blood Sampling					•			•		•				See Section 8.5 for details on sampling times
Biomarker blood sample (other BM)					•				•			•		See Section 8.8
PK blood sampling					•	•	•	•	•	•	•	•	•	See Section 8.5 for details on PK/PD sampling.
PD blood sampling	•	•	•	•	•	•	•	•	•	•	•	•	•	
Serum Pregnancy test (WOCBP only)	•	•	•	•	•					•		•		See Section 8.3.5.
Urea reduction ratio or Kt/V (local)	•				•			•		•		•		Local URR or Kt/V results obtained in the previous month to the study visit will be accepted.
Study intervention administration					•					•		•		See Section 6.1 for further details.
Dialysate effluent					•					•				See Section 8.5 for details on dialysate sampling
Clotting Score & AV access bleeding severity	•	•	•	•	•			•		•		•		See Section 8.6 for further details
Adverse events and outcome events	•	•	•	•	•	•	•	•	•	•	•	•	•	See Section 8.3; certain events will also require submission of an adjudication package to CIAC as described in Sections 8.1 and 8.2
AESI					•	•	•	•	•	•	•	•	•	See Section 8.3.8
Dialysis prescription	•				•			•		•		•		
Concomitant medications	•	•	•	•	•	•	•	•	•	•	•	•	•	

AESI = adverse events of special interest, AV = Arterio venous, BM = Biomarker, BP = Blood pressure, CIAC = Central Independent Adjudication Committee, ECG = Electrocardiogram, HD = Hemodialysis, KtV = Value used to quantify hemodialysis and peritoneal dialysis treatment adequacy, PID = participant identification code, FVIII = Coagulation Factor VIII, FIX = Coagulation factor IX, FXII = Coagulation factor XII, PK = Pharmacokinetics, PD = Pharmacodynamics(s), URR = Urea reduction ratio, vWF = Von Willebrand factor, WOCBP = Women of childbearing potential.

07 JUL 2021 Page: 18 of 90

Table 1–2: Schedule of activities, Visit V14 to visit V22

Main treatment period (24 weeks)						(24 V	veer	KS)	Comments				
					Eval	uatio	n Pe		At sites participating in the alternative PK & PD sampling group, days marked with an				
V14	V15	V16	V17	V18	V19	V20	V21	V22	asterisk are as listed in the table + 1 day (e.g V7 is Week 2, Study Day 9) ** these time points (Study Weeks and Study Days) are based on completion of either the				
13	15	17	19	21	22	23	24	25	main treatment period or the extended treatment period.				

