At the end of the hemodialysis procedure, at specified time points, the filter and line (including drip chamber/air trap) will be examined by the hemodialysis nurse (or respective appropriate personnel) after rinsing the circuit. Clotting scores will be assigned as follows:

- "0" clean filter and no visible clots in the drip chamber/air trap
- "1" traces of coagulation in the filter and/or in the drip chamber/air trap
- "2" intermediate state between "1" and "3"
- "3" fully clotted extracorporeal system resulting in an interruption of the hemodialysis session

Adequate anticoagulation is defined by a SQCS of less or equal "1".

Overall score is the highest of the individual component scores:

Inspection Site	Category 0	Category 1	Category 2	Category 3
Drip chamber (also referred to as air trap)	No visible clots in the drip chamber	Trace (e.g fibrinous ring with no clot formation on venous chamber)	Intermediate (e.g clot formation on venous chamber, more than "1" but not fully clotted)	Fully clotted system (treatment cannot continue without new setup)
Dialyzer	Clean dialyzer	Trace (e.g blood stripes affecting less than approximately 5% of the fibers seen at the surface of the dialyzer)	Intermediate (e.g blood stripes affecting approximately 5% or more of the fibers seen at the surface of the dialyzer, but not fully clotted)	Fully clotted filter

Only one (highest) score will be documented in the eCRF.

The clotting score will be recorded as specified in the SoA. The dialyzer and drip chamber/air trap will be assessed for clotting score at the end of the dialysis session on the visit day (or from a dialysis session within the visit window if the visit is not conducted on a dialysis day).

For information on PD sampling see Section 8.5.

The study sponsors reserve the right not to conduct all or part of the above-mentioned analysis.

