4.5 Data Rules

4.5.1 Analysis Dates

For the study, the following date and time window are of relevance for the analysis:

• End of Study Date

The end of the study is defined as the date the last participant completes the last protocol-defined visit/contact.

• Primary Completion Date

The primary completion date is the date when the last participant completes the main treatment period . See the below period definitions for data collection in each period.

• Main Treatment Period (actual)

The main treatment period includes a total of 24 weeks

For subjects who *did not* enter the extension period the main treatment period is defined as the period from first dose of study intervention to the last date of dose +28 days.

For subjects who *did* enter the extension period the main treatment period is defined as the period from first dose of study intervention to the administration of study intervention (and hence commencement of the extension period), at visit 22.

• Extended Treatment Period (actual)

The extended treatment period includes a total of up to 24 weeks, from study intervention administration on visit 22 until the date of last dose +28 days or date of last contact (whichever comes first).

• Post-Treatment Follow-up Period (actual)

The post-treatment follow-up period includes a total of 16 weeks. For subjects who *did not* enter the extension period, the follow up is defined as the period from the end of the main treatment period +1 day to the last contact date.

For subjects who *did* enter the extension period, the follow up is defined as the period from the end of extension period + 1 day to the last contact date.

For each subject, the following individual dates are of relevance for analysis:

• Randomization date:

The date of randomization as recorded in the IxRS system.

• Date of the first dose of study intervention:

The date of the first dose of Fesomersen or placebo will be used from the appropriate eCRF page capturing the study intervention.

Date of the earliest logically possible dose of study intervention administration will be used, in cases where the date of the first dose is missing or incomplete.

• Date of the last dose of study intervention:

The date of the last dose of Fesomersen or placebo will be used from the appropriate eCRF page capturing the study intervention.

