6.3.2.2 SQCS Analysis

The effect of Fesomersen on the clotting in the dialysis circuit will be assessed by the SQCS.

The clotting assessment will be conducted on the PD analysis set and will be presented according to treatment group. Clotting scores will be assigned as follows:

Clotting score	Definition
Clotting Score 0	Clean filter and no visible clots in the drip chambers
Clotting Score 1	For traces of coagulation in the filter and/or in the drip chambers
Clotting Score 2	Intermediate state between 1 and 3
Clotting Score 3	Fully clotted extracorporal system resulting in an interruption of the
	hemodialysis session

Table 6-1: Clotting scale score

Adequate anticoagulation is defined by an SQCS of less or equal "1".

The summary of each clotting score category will be presented in frequency and the percentage of patients by visits.

The overall score for individual subjects, which is the highest clotting score from all visits per data scope, will also be summarized. The overall clotting score will be analyzed for treatment comparison between each Fesomersen dose groups and placebo group using the Wilcoxon Rank Sum test.

The difference in the mean of SQCSs during the main treatment period between each of the Fesomersen groups and the placebo group will be displayed together with the corresponding 90% (and 95%) confidence intervals applying ANOVA with treatment group as factor.

Furthermore, the difference in the proportion of hemodialysis sessions with adequate anticoagulation during the main treatment period between each of the Fesomersen dose groups and the placebo group will be summarized with the corresponding 90% (and 95%) confidence intervals using the unstratified exact method with the standardized test statistic and inverting a two-sided test (Agresti and Min, 2000) as exploratory analysis.

Frequency of dialyzer filters usage will be analyzed through descriptive statistics.

Most severe clotting category

In order to examine the correlation of FXI activity level and clotting, a separate summary on the most severe clotting category will be provided for patients with average FXI activity ≤ 0.1 , ≤ 0.2 , ≤ 0.3 , ..., ≤ 1.0 U/mL for Fesomersen treated patients only.

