6.4.1 Analysis of the Primary Safety Variable

The primary analysis is based on a descriptive proportion of subjects with primary endpoints (independently adjudicated) based on SAF analysis set and PA data scope. For each treatment and bleeding category, participants reporting more than one bleeding event will be counted only once using the highest severity. The frequency and percentage of participants with bleeding will be reported where the denominator will be total number of participants in each treatment group.

Estimand for the Primary Safety Endpoint:

The five attributes of the estimand are as follows:

- **Population:** The population consists of ESRD patients as described by the inclusion/exclusion criteria given in study protocol.
- Variable: The incidence of the composite of MB, CRNMB, events during the main treatment period, as assessed by the CIAC
- Treatment: Three dose groups of Fesomersen or placebo on top of standard of care
- Intercurrent events:
 - Unblinding to study intervention: the study allows unblinding of treatment assignment if the investigator deems necessary when related a bleeding or major surgery occur regardless of whether such an event occurs (treatment-policy strategy)
 - Early definitive discontinuation of study intervention or death or kidney transplant: until the occurrence of the intercurrent event (while on treatment strategy)
 - Dose reduction: regardless of whether such an event occurs (treatment-policy strategy).
- **Population-level summary:** Incidence proportion of subjects with an event by study intervention group and differences between Fesomersen treatment groups and placebo group. For the incidence proportions the exact binomial two-sided 95% confidence interval using Blaker's method will be provided. For the difference in incidence proportions the two-sided 95% confidence interval will be presented using the unstratified exact method with the standardized test statistic and inverting a two-sided test (Agresti and Min, 2000).

6.4.1.1 Additional Primary Safety Endpoint(s) Analysis:

Estimand for Time to Event Safety Endpoint:

The attributes constituting the estimand for this endpoint are the following:

- **Population:** The population consists of ESRD patients as described by the inclusion/exclusion criteria given in study protocol.
- Variable:
 - Time from first dose of intervention to MB and CRNMB events (in alignment with ISTH guidelines) up until 28 days after last study intervention

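### The exact interval for the proportion of adequately anticoagulated dialysis sessions treats 10 or 11 sessions from one participant as independent, so it is too narrow

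*SAP*

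**What the plan says.** SAP 6.3.2.2 counts a session as adequately anticoagulated when the semi-quantitative clotting score (SQCS) is 1 or less. For each dose group against placebo it plans to summarise "the difference in the proportion of hemodialysis sessions with adequate anticoagulation during the main treatment period". The 90% and 95% intervals are obtained "using the unstratified exact method with the standardized test statistic and inverting a two-sided test", and the analysis is labelled exploratory.

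Two other comparisons stand in the same section:

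- A Wilcoxon test on one value per participant: "The overall score for individual subjects, which is the highest clotting score from all visits per data scope".
- A difference in mean SQCS, with "confidence intervals applying ANOVA with treatment group as factor". The section does not say whether the record entering this ANOVA is a session or a participant.

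The number of sessions comes from Protocol 1.3, row "Clotting Score & AV access bleeding severity". Two passages bear on whether Visit 22 belongs to the main period. Under SAP 4.5.1, for participants who continue, that period runs from first dose "to the administration of study intervention (and hence commencement of the extension period), at visit 22". Under Protocol 8.6.2, the dialyzer and drip chamber "will be assessed for clotting score at the end of the dialysis session on the visit day", which is after that dose.

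SAP 6.4.1 uses the same exact method for the difference in bleeding proportions, but there "participants reporting more than one bleeding event will be counted only once using the highest severity".

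**The concern.** The exact two-binomial method takes a count of successes out of a number of independent trials in each arm. In 6.4.1 the trial is a participant, so the condition is met. In 6.3.2.2 the trial is a session, and each participant supplies up to 11 of them.

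The documents give reasons to expect these sessions to resemble each other. Participants stay on their own provider's dialysis regimen, including heparin, and ASA use is meant to stay constant (Protocol 4.1). Heparin use for dialysis maintenance is summarised as a baseline characteristic (SAP 6.1.8). Visits 18 to 22 are only a week apart (days 141 to 169).

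If sessions are positively correlated, the stated 90% and 95% levels are not achieved, and a dose can look separated from placebo on circuit clotting by chance. The primary analysis is performed to speed Phase 3 dose selection (Protocol 4.1), and less circuit clotting was reported for the parent compound (Protocol 2.2.3.2). The result is therefore likely to be read, even though no decision rule depends on it.

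**Working it through.** The documents state no width, power or sample size for this analysis, so there is no figure of the plan to reproduce.

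**Step 1. Sessions per participant (m).** Table 1-1 schedules the score in the main period at V5, V8, V10 and V12, which is 4. Table 1-2 schedules it at V14, V16, V18, V19, V20, V21 and V22, which is 7. In the copy read, the row labels of Table 1-2 are lost, and the row was identified by its comment pointing to Section 8.6. So m = 4 + 7 = 11, or 10 if the V22 score falls in the extension. Early leavers contribute fewer.

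**Step 2. Width factor.** Design effect = 1 + (m − 1) × ICC. The standard error is understated by its square root. The ICC is assumed. Example: m = 10, ICC 0.1 gives √(1 + 9 × 0.1) = √1.9 = 1.38.

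**Step 3. Coverage.** Coverage = 2Φ(z / √design effect) − 1, with z = 1.960 (95%) or 1.645 (90%). Example: 1.960 / 1.38 = 1.42, giving 84%.

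| Assumed ICC | Width factor, m = 10 / 11 | Coverage of 95% interval | Coverage of 90% interval |
|---|---|---|---|
| 0.05 | 1.20 / 1.22 | 90 / 89% | 83 / 82% |
| 0.1 | 1.38 / 1.41 | 84 / 83% | 77 / 75% |
| 0.3 | 1.92 / 2.00 | 69 / 67% | 61 / 59% |
| 0.5 | 2.35 / 2.45 | 60 / 58% | 52 / 50% |

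Put another way, 60 completers per arm give 600 sessions at m = 10. These carry the information of 600 / 1.9 = 316 independent sessions at ICC 0.1, and 600 / 5.5 = 109 at ICC 0.5.

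**Step 4. Simulated coverage.** The model was beta-binomial with 60 participants per arm and 20,000 trials per setting, using the score interval (the standardized statistic that the exact method inverts). Coverage of the nominal 95% interval was about 95% at ICC 0, 83–85% at 0.1, 67–70% at 0.3 and 57–59% at 0.5. This agrees with the formula.

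**Step 5. Exact method against score interval.** At 660 sessions per arm and 85% against 75% adequacy, the exact 95% interval is 8.72 points wide and the score interval 8.57. The ratio is 1.018, so the exact method's conservatism adds about 2%. It could offset a design effect of 1.018² = 1.035, that is an ICC of about 0.035 / 9 = 0.004.

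**Step 6. Exclusion of zero with no true difference.** The simulation had 72 per arm. One sixth left early (72 to 60, the documents' figures) with 1–9 sessions (assumed), and the rest had 10. The planned method was represented by the pooled score statistic at zero difference.

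| Assumed ICC | Planned 95% interval excludes zero |
|---|---|
| 0.05 | 10% |
| 0.1 | 15% |
| 0.3 | 30–31% |
| 0.5 | 40–41% |

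Results hardly changed between assumed adequacy of 70%, 85% and 95%. A t-interval on per-participant proportions excluded zero in 4.6–5.3% of trials throughout.

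**Step 7. Half-widths at 85% adequacy.** Sessions per arm: 60 × 10 + 12 × 5 = 660. Planned half-width: 1.96 × √(2 × 0.85 × 0.15 / 660) = 3.85 points. The per-participant analysis gives 5.5, 7.4 and 8.8 points at ICC 0.1, 0.3 and 0.5.

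**The case against.** The strongest objection concerns importance. The interval is exploratory, Protocol 9.1 plans no hypothesis testing, and the primary endpoint is untouched. Section 6.3.2.2 also provides score categories by visit and a participant-level Wilcoxon comparison, neither of which depends on independent sessions. This stands, and it limits the priority of the point. It does not make the interval right, because a descriptive 95% interval should still cover at about its stated rate. The SAP is also not free of testing: Section 4.1 sets a two-sided 10% level.

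Second, the size rests on an assumed ICC. Nothing in the documents favours 0.1–0.5 over 0.05, where the factor is only about 1.2. This also stands. Only the direction is established, and strictly only for an ICC above about 0.004, because the exact method is slightly conservative.

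Third, the session count could be lower. In the alternative sampling group (about 24–40 participants), V5 is on a non-dialysis day with a zero-day window, so its score may be missing. With both V5 and V22 dropped, m = 9 and the factor is 1.34 at ICC 0.1 and 2.24 at ICC 0.5, which changes little.

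Fourth, programming details sit in a separate output specification (SAP Section 1) that was not available. It might settle the unit of the ANOVA. It cannot make the method named in the SAP suitable for repeated sessions.

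Fifth, the per-participant remedy changes the target slightly and can cost some precision. In the Step 7 setting the session-weighted mean cluster size is (60 × 100 + 12 × 31.67) / 660 = 9.67. A session-weighted, cluster-adjusted half-width at ICC 0.1 is then 3.85 × √(1 + 8.67 × 0.1) = 5.3 points, against 5.5. Most of the move from 3.85 is therefore the correlation correction.

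**Conclusion.** The concern holds. As written, the plan applies a method for independent binomials to repeated sessions of the same participants, and nothing in either document corrects for it. The intervals will be too narrow by about 1.4-fold at ICC 0.1 and about 2.4-fold at ICC 0.5. The mechanism and direction are certain for any correlation of practical size; the amount depends on an ICC that the documents do not give.

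The fault is confined to this one exploratory comparison. The Wilcoxon test and the primary bleeding analysis are not affected. The mean-SQCS ANOVA shares the fault only if it is run on sessions. The plan should be corrected, but no primary conclusion depends on it.

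**What to change.** In SAP 6.3.2.2:

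- Make the participant the unit. Compute each participant's proportion of scored main-period sessions with SQCS of 1 or less, and report the difference in group means with t-based 90% and 95% intervals.
- If weighting by session is preferred, use a GEE with identity link, or a cluster-robust risk difference, with participant as the cluster.
- State that the mean-SQCS ANOVA uses one mean per participant.
- State whether the V22 score counts as main period for participants who continue.

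A participant-level summary fits the existing plan: Protocol 9.4.6.3 already foresees averaging measurements over the evaluation period.

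The cost is two or three sentences and a different SAS procedure, with no new data. Intervals become wider. The per-participant version weights participants equally rather than by number of sessions, so the estimate can shift slightly if early leavers differ. SAP 6.5 indicates that the primary analysis was complete before the current SAP version, so the change would apply to the final analysis and any re-reporting, through the amendment route in SAP 4.6.

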that the 200 mg regimen was noninferior, and the 300 mg regimen of FXI-ASO was superior to enoxaparin. These data would support the investigation of a higher FXI suppression level of approximate 20% remaining FXI activity.

Spontaneous bleeding, including clinically significant bleedings, do not show dependency on lower levels of FXI in the above cited publications and other published literature. In addition, no increase in number of clinically significant bleeding under treatment with the parent compound BAY 2306001 was seen in two studies with ESRD patients.

With a view on potential clinical efficacy and considering safety, reduced FXI levels of less than 15% to approximately 50% remaining activity are justified for the current study. The three doses of 40 mg, 80 mg, and 120 mg BAY 2976217 have been selected to optimally cover for this range.

A protocol-defined option for dose step-down for the 120 mg dose level (see section 4.1) is provided to the DMC. Also, the predicted steady-state FXI levels with 120 mg once monthly dosing are expected to be similar to those achieved with the 300 mg dose level in the TKA study (ISIS 416858-CS3) in which no increased clinically significant bleeding was observed.

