For major surgery (defined as a surgical procedure involving an organ within the cranium, chest, abdomen, or pelvic cavity) including kidney transplant, prophylaxis with an antifibrinolytic such as aminocaproic acid or tranexamic acid could be considered with careful consideration of appropriate use and dose in ESRD (consult the prescribing information). Prophylaxis with antifibrinolytics have been used in both congenital FXI deficiency (42) and those without FXI deficiency (49). The administration of low-dose recombinant FVIIa along

07 JUL 2021 Page: 47 of 90

with tranexamic acid was also reported as a prophylaxis option in patients with severe FXI deficiency undergoing surgery (50, 51).

Factor replacement therapy may also be considered prophylactically, and in any case should be on stand-by during surgery. Factor replacement is typically with FFP, as FXI concentrate replacement is not universally available. Careful attention to and management of ESRD participant's volume status when infusing blood product is essential. If uremic platelet dysfunction is suspected, adjunctive therapy could also be considered (e.g., desmopressin, conjugated estrogens).

Based on recommendations in congenital FXI deficiency (42), replacement therapy with FFP (or FXI concentrate infusions, if available) should be targeted to reach a trough FXI level of 0.45 U/mL (or higher) for approximately 7 days after surgery. The investigator should recognize that the half-life of circulating Factor XI is approximately 50 hours when considering the potential need for re-administration, particularly of FFP or FXI concentrate. Additionally, the time necessary to obtain a Factor XI concentration locally (if the investigator chooses to unblind the participant) and to infuse FFP should be taken into consideration.

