6.3.2.1 The PD profile

The effect of Fesomersen on PD profile will be assessed on maximum change in FXI activity levels, FXI antigen levels, PT, INR, aPTT, d-dimer, TAT, and F1.2 levels during the main treatment period by treatment group in PD analysis set.

Change and percent change from baseline FXI activity levels, FXI antigen levels, PT, INR, aPTT, d-dimer, TAT, and F1.2 levels will be summarized by treatment and visit separately. Individual results will be presented in data listings by treatment. Figures of the mean levels of all PD parameters (FXI activity and antigen, PT, INR, aPTT, d-dimer, TAT and F1.2) as well as change and percent change from baseline will be provided by treatment group, and scheduled visit.

Change and percent change from baseline in FXI activity levels, FXI antigen levels, PT, INR, and aPTT will be compared between each of the study intervention group and pooled placebo group using the Wilcoxon Rank Sum test.

Frequency and percent of patients with average FXI activity $\leq 0.1, \leq 0.2, \leq 0.3, ..., \leq 1.0 \text{ U/mL}$ during each visit with PK/PD measurements up to last dose + 28 days will also be provided.

The incidence and events for any aPTT>160s will be summarized by treatment and visit.

For all treatments where at least one subject with at least one confirmed ADA formation is included, the PD parameters. in plasma will be displayed including supplemental information about the ADA titer. Individual subjects with confirmed ADA formation will be indicated by different colors and symbols.

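### The SAP's FXI-versus-clotting summary sets a worst-over-visits score against nested, undefined average-FXI categories in treated patients only, which attenuates and may mask a real relation

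*SAP*

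**What the plan says.** The last paragraph of SAP 6.3.2.2 gives its purpose as "In order to examine the correlation of FXI activity level and clotting". The method is that "a separate summary on the most severe clotting category will be provided for patients with average FXI activity" at or below 0.1, 0.2, 0.3 and so on to 1.0 U/mL, "for Fesomersen treated patients only". No coefficient, model or visit-level pairing is specified.

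- **Clotting variable.** The nearest definition, earlier in the same section, is the overall score, "which is the highest clotting score from all visits per data scope".
- **FXI variable.** No averaging window is given. SAP 6.3.2.1 uses the same cut-points for average FXI activity "during each visit with PK/PD measurements up to last dose + 28 days", which reads as per visit.
- **Data scope.** None is named for this summary. SAP Table 5-2 lists the maximum-change FXI endpoints under the overall (OA) scope. Under SAP 4.5.2 the PA, TA and OA scopes all begin at the first administration.
- **Visits.** In the main treatment period the Schedule of Activities (Protocol 1.3) places "Clotting Score & AV access bleeding severity" at V5, V8, V10, V12, V14, V16 and V18 to V22. Protocol Table 8-1 has PD blood sampling at each of these visits.
- **FXI range.** Protocol 4.3 states that "reduced FXI levels of less than 15% to approximately 50% remaining activity are justified for the current study". Protocol 8.2.1.3 cites a reference range of 0.73 to 1.45 U/mL and says that the "half-life of circulating Factor XI is approximately 50 hours".

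**The concern.** A table meant to show a relation should set each outcome beside the exposure that applied when it occurred, in categories that can be compared. This one departs from that in four ways.

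1. **Timing.** The worst of many scores may come from a session at which FXI was quite different from the participant's average.
2. **First-dose session.** Outside the alternative sampling group, dosing falls within 15 minutes of the start of dialysis (Protocol 6.1) and the score is taken at the end of the session (Protocol 8.6.2). The V5 score therefore lies inside every scope that starts at first dose, at essentially untreated FXI.
3. **Nesting.** A participant averaging 0.1 U/mL is counted in all ten rows, so differences between rows are diluted.
4. **No placebo.** Most of the unsuppressed FXI range is missing.

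Doses were chosen by target FXI level (Protocol 4.3), and the primary analysis is meant to speed Phase 3 dose selection (Protocol 4.1). This is the only analysis that the SAP itself specifies between FXI level and circuit clotting, so a weakened picture could lead a reader to underrate the relation.

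**Working it through.** The plan gives no expected result for this summary, so there is no planned figure to reproduce. The documents give no rates for the clotting score (SQCS) either. Every rate and FXI distribution below is an assumption, and ranges are shown.

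**Step 1: FXI at the end of the V5 session.** With a half-life of 50 h, and synthesis stopping completely at injection (an upper limit), the fall after t hours is 1 − 2^(−t/50). For an assumed 4 h this is 5.4%, and for 6 h it is 8.0%. The V5 score belongs to near-baseline FXI.

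**Step 2: taking the worst score.** With session risk p of a score ≥2 and 11 independent scored sessions, P(worst ≥2) = 1 − (1 − p)^11.

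- p = 10% gives 68.6% and p = 30% gives 98.0%. A 3-fold contrast becomes 0.980/0.686 = 1.43.
- If the 10% participant has 30% risk at V5, 1 − 0.9^10 × 0.7 = 75.6%, and the contrast becomes 0.980/0.756 = 1.30.
- p = 1% gives 10.5% and p = 10% gives 68.6%. A 10-fold contrast becomes 0.686/0.105 = 6.5, so compression is modest when high scores are rare.

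**Step 3: nesting.** Assume average FXI of 0.50, 0.30 and 0.15 U/mL in the three doses (SD 0.15, 0.10, 0.07), worst of 10 visits, and session risk logit-linear in FXI from 5% at 0.1 to 30% at 1.0. Keeping the worst score, disjoint bands run from 37.6% (≤0.1) to 82.0% (0.6–0.7), a ratio of 2.2. Nested rows run from 37.6% to 55.7% (≤0.7), a ratio of 1.5.

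If counts are printed, a band can be recovered by differencing adjacent rows. With risks of 10% to 50%, the ≤0.6 row holds 91.5% of patients at 78.6% and the ≤0.7 row holds 97.0% at 79.6%. Then (97.0 × 79.6 − 91.5 × 78.6)/(97.0 − 91.5) = 96.2%, against 97.0% computed directly. The gap is rounding.

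**Step 4: the whole layout, same FXI assumptions.**

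| Session risk of score ≥2, FXI 0.1 to 1.0 | Nested rows, ≤0.1 to ≤1.0 | Ratio | Ratio if 2 of 10 scores precede the FXI fall | Session-level disjoint bands, 0.6–0.7 v ≤0.1 |
|---|---|---|---|---|
| 1% to 30% | 8.3% to 25.5% | 3.1 | 1.13 | 9.9 |
| 2% to 20% | 16.7% to 32.4% | 1.9 | 1.19 | 4.7 |
| 5% to 30% | 37.6% to 56.7% | 1.5 | 1.13 | 3.4 |
| 10% to 50% | 62.0% to 80.2% | 1.3 | 1.06 | 3.2 |

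Only V5 clearly precedes the fall, so two such scores is the pessimistic end. One gives a ratio between the two columns. Adding between-patient variation (SD 1 on the logit scale, 5% to 30%) gives nested rows of 42.1% to 56.7% (1.35) and session-level bands of 6.7% to 19.7% (2.9).

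**Step 5: a model with an onset phase.** Assume 72 participants per dose, steady-state FXI of 0.50, 0.35 and 0.20 of baseline, an onset time constant of 20 days, 11 scored sessions including V5, 15% dropout and some between-patient spread in FXI.

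| Session risk at FXI 0.2 / 1.0 | Nested, ≤1.0 v ≤0.3 | Same-visit bands, >0.6 v ≤0.3 |
|---|---|---|
| 10% / 30% | 1.09 | 2.4 |
| 5% / 30% | 1.26 | 4.3 |
| 2% / 20% | 1.53 | 6.7 |
| 1% / 10% | 1.62 | 7.1 |

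With V5 excluded, the nested ratios run from 1.09 to 1.55 and the same-visit ratios from 2.0 to 4.5.

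**Step 6: placebo.** Under the Step 3 assumptions about 3% of treated patients average above 0.7 U/mL. Adding placebo (assumed mean 1.0, SD 0.2) moves the nested ≤1.0 row only from 56.7% to 61.7%. It raises the share of patients in the disjoint 0.9–1.0 band from 0.1% to 4.8%.

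**The case against.** The strongest reply is that this is one descriptive, exploratory PD table in a study with no planned hypothesis testing (Protocol 9.1), and that the question is partly covered elsewhere. SAP 6.3.2.2 already compares mean scores and the proportion of adequately anticoagulated sessions between each dose and placebo. SAP 6.3.1 foresees exposure-response modelling in a separate document, if applicable. This stands as a limit on importance. It does not supply the missing analysis: the arm comparisons address dose rather than FXI level, and whether the modelling will cover the clotting score cannot be seen.

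A reader might go further than the documents allow in several ways.

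- **That the table hides even a strong relation, or must look flat.** It need not. The end-to-end nested ratio exceeded 1 in every scenario, and with uncommon high scores a 3.1-fold gradient remains.
- **That nested rows cannot be contrasted.** They can be differenced if counts are shown, so nesting mainly blurs the display. The mismatch in time cannot be undone from the table.
- **That FXI is a period average, or that the PA scope applies.** Neither is stated. A per-visit average would not settle the matter, because a category that changes by visit does not pair with one worst score.
- **That early stoppers distort the table materially.** In the Step 5 model at 10% / 30%, moving dropout from 0% to 15% changed the nested rows only from 74–83% to 74–81%.
- **That this table decides the Phase 3 dose.** Protocol 4.1 ties dose selection to the primary analysis as a whole.

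It is also fair to say that setting nested ratios beside session-level ratios changes unit, pairing and top category together. The gap should not be credited to any single feature. Nesting alone accounts for 1.5 against 2.2 in Step 3.

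**Conclusion.** The concern holds as one of attenuation. For its stated purpose, the summary uses a worst score that is not matched in time to FXI and can come from the first-dose session. It blurs row contrasts by nesting, omits most of the unsuppressed range, and leaves the averaging window and data scope open. A real FXI-clotting relation would be weakened and may be masked.

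Under the assumed rates the nested-row ratio ran from about 1.06 to 3.1. Session-level disjoint bands gave about 2.4 to 9.9 with V5 not separated, and about 2.0 to 4.5 with V5 excluded (onset model only). Where the trial would fall depends mainly on how common scores of 2 or more are, and the documents do not say. The omission of placebo is contributory: the doses are meant to span below 15% to about 50% remaining activity, so a relation within treated patients can still appear. This is a worthwhile, inexpensive improvement to an exploratory summary. It does not affect the primary endpoint or the dose-versus-placebo clotting comparisons.

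**What to change.** Replace the last paragraph of SAP 6.3.2.2 with a session-level summary:

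- Pair each scored session with FXI activity from the same visit, naming the sample to use where there are several (pre-dose where available).
- Use non-overlapping bands: ≤0.1, >0.1–0.2, >0.2–0.3 U/mL and so on, with an open top band.
- Report, per band, the number of sessions and participants and the proportions of sessions with SQCS ≤1 and ≥2.
- Show treated participants and placebo separately and together.
- Show V5 apart as the first-dose session.
- State the data scope. If follow-up is included, note that FU2 and FU3 are scored without PD sampling.
- Make any interval allow for repeated sessions per participant. A GEE logistic model on FXI is one option, not a requirement.

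The cost is one SAP paragraph and one reprogrammed table, from data already scheduled. SAP 6.5 records that the primary analysis has been completed, so the table should be labelled as specified after it. FXI level will remain partly confounded with time on study and with arm, so the summary stays descriptive.
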